8.4 ECGs

Summary statistics by treatment of Heart Rate (b/min), PQ interval (msec), QT interval (msec), QTcB (msec) and ECG interpretation will be provided along with summary of the change/shift from baseline at each available timepoint (Day 3, Day 7, Day 14, Day 21, end of treatment, and hospital discharge). Even if ECG are collected at screening and the protocol mention changes from screening, baseline and changes from baseline will be provided: this means that, if for some reason the screening assessment is done after treatment start date (by mistake or any reason), the value will not be considered in the analysis, since the value will not be flagged as "Baseline" (as defined in section 3.2.2).

In addition, summary statistics of the number and frequency of patients with an alteration and the type of alteration will be provided by treatment arm and overall at each available timepoint.

The following graphical representations will be provided for all quantitative ECG values:

- Spaghetti plot of individuals' observed data and change from baseline (with x-axis marked by days relative to start of actual treatment);
- Boxplot for values and changes from baseline by actual treatment at each timepoint.

Listings showing ECG results, as well as abnormal clinically significant ECG results will be provided.

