2. SCHEDULE OF EVALUATION

The grid below summarizes the study schedule of the trial. For all measurements, the actual date and time of assessment, including date of sampling, will be recorded in the Source Document and/or eCRFs. Timeframe for each assessment is also shown in the grid below.

Days (windows)	Screening (day-1 or 1)	Randomization and baseline assessments ¹	Day 1	Day 2 (±8h)	Day 3 (±8h)	Day7 (±1)	Day 14 (±2)	End of Treatment ²	Extubation to Hospital Discharge (every 48h±8h)	Day 28 (±2) and Hospital Discharge ¹⁹	Day 60
ELIGIBILITY											
Informed consent signed	X										
Demo-graphics, Medical History, Disease-Specific Information, allergies	X										
Pregnancy test ²	X										
STUDY INTERVENTION											
Randomization		X									
IMP administration ³			Daily through day 14 with the option to extend to day 21								
STUDY PROCEDURES											
Vital signs (RR, HR, MAP)			Daily through extubation				X				
PaO ₂ (or SaO ₂), FIO ₂	X		Daily through extubation				X	X			
PaCO ₂			Daily through extubation								
Mechanical ventilation parameters ⁴			Daily through extubation								
SOFA score			Daily through extubation								
Neuromuscular blocking agents, inhaled vasodilators ⁵			Daily through extubation								
Prone positioning ⁶			Daily through extubation								
Vasoactive medications ⁷			Daily through extubation								
ECMO ⁸			Daily through extubation								
CPAP attempts ⁹			Daily through extubation								
Chest imaging ¹⁰	X	X	X	X	X	X					
Biomarkers ¹¹		X		X	X	X					
Reintubation ¹²									X		
Other clinical events ¹³									X		
Follow up ¹⁴										X	
SAFETY TESTS											
Adverse events	↔										
Concomitant medications	↔										
Safety hematology and	X				X	X	X	X		X	

Days (windows)	Screening (day-1 or 1)	Randomization and baseline assessments ¹	Day 1	Day 2 (-8h)	Day 3 (-8h)	Day 7 (±1)	Day 14 (±2)	End of Treatment ²¹	Extubation to Hospital Discharge (every 48h±8h)	Day 28 (±2) and Hospital Discharge ¹⁹	Day 60
biochemistry ¹⁵											
eGFR ¹⁶	X			X	X	X	X			X	
Hepatic function ¹⁷	X			X	X	X	X				
ECG	X			X	X	X	X				X ²¹
CCI											

1. Baseline and initiation of IMP (day1) may coincide
2. In females of childbearing potential, only date will be required
3. Study product will be administered every 8 hours (q8h) for 14 days, and optionally up to 21 days
4. Mode of ventilation, TV, mean airway pressure, plateau airway pressure, PEEP
5. Use or not of neuromuscular blocking medications and/or inhaled vasodilators

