In clinical trials with oral tablets, reparixin was administered for 21 consecutive days followed by 7 days of drug holiday before the next cycle. Reparixin was rapidly absorbed (median T_{max} 1 hr). Reparixin systemic exposure (C_{max} and AUC_{last}) did not change from day 1 to day 21, indicating the absence of accumulation over the dosing period. Also, T_{1/2} did not change from day 1 to day 21, with a median value of about 2 hrs. Once absorbed, reparixin is highly bound to proteins as only <0.1% to 0.2% of total reparixin is available as unbound (free) drug. Reparixin was rapidly metabolized to DF2243Y, DF2188Y and ibuprofen. For all three metabolites systemic exposure was similar on both day 1 and day 21 within the observed inter-subject variability. The T_{1/2} of all three metabolites appeared to remain about the same from day 1 to day 21.

To investigate the PD characteristics of reparixin, the effect of the drug in inhibiting IL-8- mediated Neutrophils Extracellular Traps (NET) release by human PMN in the whole blood of healthy volunteers was assessed. Reparixin blocked IL-8-induced NET formation in a concentration dependent manner, with the inhibition (40%) becoming statistically significant at 5 µg/mL and reaching near completeness (about 90%) at 25 µg/mL which corresponds to the total blood concentration (equivalent to a free unbound concentration of 100 nM) that is reached at the steady state (C_{ss}) by IV infusion or by repeated oral administration.

Reparixin has some potential *in vitro* for a non-competitive inhibition of the human hepatic enzyme CYP3A4 that is involved in the metabolism of cyclosporine A, tacrolimus and rapamycin. However, since inhibition

is evident at concentrations far higher than the free plasma concentration of reparixin at steady state in humans, it is predicted that the clinical relevance of such inhibition is minor. Indeed, reparixin does not affect, to a clinically relevant extent, the activity of CYP3A4 and CYP2C9 (enzyme involved in reparixin metabolism), as revealed by an interaction study where the PK of midazolam and tolbutamide (probe substrates for these enzymes) was evaluated in healthy subjects receiving single oral doses of the probes alone or in combination with reparixin.

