Prior and Concomitant medications	
At screening: recording of drug name, indication, total daily dose, dose unit, route, start and end dates
 
During hospital stay: recording of any change of already recorded, or new concomitant medications

Lung function	
 - Peripheral arterial oxygen saturation (SpO₂; %) - Partial pressure of oxygen (PaO₂; mmHg) - Partial pressure of carbon dioxide (PaCO₂; mmHg) - Mean airway pressure (cm H₂O) - Plateau airway pressure (cm H₂O) - PEEP (cm H₂O) - Tidal volume (mL) - Fraction of inspired O₂ (FIO₂; 0.21 to 1) - PaO₂/FIO₂ (mmHg); SpO₂ may be used in place of PaO₂ if arterial sample is not available
IMV/ECMO	
 - Endotracheal intubation - Tracheostomy tube 
Extracorporeal Membrane Oxygenation Duration of IMV or ECMO to be recorded (days)

SECONDARY INFECTIONS	
Defined as:
 
 1) New (occurring after the first IMP intake) infection in a previously known to be sterile site, including blood, body fluid or tissue. 2) New pathogen isolated from cultures of biological samples known to be previously infected
ECG	
ECG after the subject has been lying quietly for 5 minutes.
 
The following to be recorded:
 
 - overall assessment for the presence of alterations (no / yes), - presence of: arrhythmia, conduction abnormalities; ST-segment elevation / depression; T-wave alterations; - HR (bpm) - PQ interval (msec); - QT/QTc (Bazett formula; msec) 
Clinically significant abnormalities should be marked in the ECG-CRF (no / yes, specify) and also reported as an AE

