3.6 Safety endpoints

- Haematology/biochemistry tests change from screening to day 3±8h, 7±1, 14±2, 21±2 (if still receiving reparixin), 28±2 visits and at hospital discharge [by visit]
- eGFR, absolute value and change from screening to day 3±8h, 7±1, 14±2, 21±2 (if still receiving reparixin), 28±2 visits and hospital discharge [by visit]
- Hepatic Function (ALT/AST, total/direct bilirubin), absolute values and change from screening to day 3±8h, 7±1, 14±2, 21±2 (if still receiving reparixin) visits and at hospital discharge [by visit]

Standard/Forms/Template				
Title		Statistical Analysis Plan Template		
Code		Version	Effective Date	Page
PPD		01	29 Aug 2022	23 of 78

- ECG/rhythm analysis changes from screening to day 3 ± 8 h, 7 ± 1 , 14 ± 2 , 21 ± 2 (if still receiving reparixin), 28 ± 2 visits and hospital discharge. [by visit]
- Incidence of secondary infections defined as new (occurring after the first IMP intake) infection in a previously known to be sterile site, including blood, body fluid or tissue, or new pathogen isolated from cultures of biological samples known to be previously infected by day 28 [study day: see section 11.1.1]
- Incidence of TEAEs and TESAEs from the beginning of study treatment to up to the end of study participation.
- Vital Signs change from baseline to daily assessment through extubation (namely, day 1, day 2, day 3, day 7, day 14, day 21) [study day: date/time]

4. Statistical Analysis

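### Bazett is the only QT correction planned, so heart-rate changes leak into the QTc summaries; a Fridericia value can be derived from data already recorded

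*SAP*

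**What the plan says.** Protocol 6.5 lists what is taken from each ECG: an overall assessment, the type of any alteration, heart rate, PQ interval and "QT/QTc (Bazett formula; msec". SAP 8.4 plans "Summary statistics by treatment of Heart Rate (b/min), PQ interval (msec" and continues with "QT interval (msec), QTcB (msec) and ECG interpretation will be provided along with summary of the change/shift from baseline". It adds spaghetti plots and boxplots of values and changes, and listings that include clinically significant abnormal ECGs. Neither document names a second QT correction.

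The safety endpoint in SAP 3.6 is worded as "ECG/rhythm analysis changes from screening to day" 3 and later visits. QTc is one parameter summarised under it, with no hypothesis and no categorical threshold.

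ECGs are scheduled by study day (Protocol 2) and analysed by nominal visit whatever the study day (SAP 3.2.1). No visible text ties an ECG to a dose. On dosing, the schedule notes say: "Study product will be administered every 8 hours (q8h) for 14 days, and optionally up to 21 days". For oral tablets, Protocol 2.4 says "Reparixin was rapidly absorbed (median T_{max} 1 hr", and that the half-life "did not change from day 1 to day 21, with a median value of about 2 hrs".

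**The concern.** Bazett divides QT by the square root of the RR interval; Fridericia divides by the cube root. If QT varies with rate roughly as the cube root, Bazett reads too high at fast rates, and QTcB falls as a patient's heart rate settles even though repolarisation has not changed. Patients enter this trial on invasive ventilation and many will be recovering over the weeks in which ECGs are repeated, so heart rate may well change between baseline and follow-up.

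Two things are at stake. First, a within-arm or individual change in QTcB cannot be read as a change in repolarisation. Second, the trial's objective is faster clinical recovery on reparixin. If that also lowers heart rate more on reparixin, QTcB falls more in that arm and could offset a real prolongation.

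**Working it through.** The plan states no QTc figure, so there is nothing to reproduce. The heart rates and the reference QTcF below are assumptions.

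**1. Formulas.** With RR = 60/HR in seconds:
- QTcB = QT / RR^(1/2)
- QTcF = QT / RR^(1/3)
- hence QTcB / QTcF = RR^(-1/6) = (HR/60)^(1/6)

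**2. QTcB at a constant QTcF of 420 ms.**

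| HR (bpm) | QTcB (ms) |
|---|---|
| 80 | 440.6 |
| 85 | 445.1 |
| 90 | 449.4 |
| 100 | 457.3 |
| 110 | 464.6 |
| 120 | 471.4 |

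**3. Within-patient artefact (true change zero).**
- 90 to 80 bpm: about -9 ms
- 110 to 85 bpm: 445.1 - 464.6 = -19.5 ms
- 120 to 80 bpm: 440.6 - 471.4 = -30.8 ms

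The reference value matters little. For 110 to 80 bpm the fall is 22.9 ms at QTcF 400, 24.0 ms at 420 and 25.2 ms at 440.

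**4. Between-arm artefact.** A mean of 90 bpm in one arm and 85 in the other gives 449.4 - 445.1 = 4.3 ms. A gap of 90 against 80 gives about 9 ms. With equal heart rates it is zero.

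**5. Masking.** Suppose placebo is at 90 bpm with QTcF 420 ms and reparixin is at a lower rate. QTcB is equal in the two arms when the reparixin QTcF is 420 × (90/HR)^(1/6):
- HR 85: 424.0 ms, so a true prolongation of 4.0 ms disappears
- HR 80: 428.3 ms, so a true prolongation of 8.3 ms disappears

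**6. Timing of ECGs.** The Day 3 window of ±8 h is 16 h wide, which is two full dosing intervals. In a one-compartment model at steady state with Tmax 1 h, half-life 2 h (k = 0.347/h, ka = 2.19/h) and an 8 h interval, an ECG at a random time is at 80% or more of peak about 20% of the time and below half of peak 59% of the time. Varying half-life over 1.5 to 3 h and Tmax over 0.5 to 2 h moves the share below half of peak from 28% to 74%.

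**The case against.** The strongest reply is randomisation. The trial is double-blind, 1:1 and placebo-controlled, and SAP 8.4 reports by treatment, so a heart-rate fall shared by both arms cancels in the comparison. That stands. It does not help the within-arm changes, individual plots and listings, and it does not help if heart rate differs between arms.

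Nothing in the documents predicts a 5 bpm gap. That is also true, but chance can supply one. With 30 per arm and an assumed heart-rate SD of 15 to 20 bpm, the standard error of the arm difference is SD × √(2/30), or 3.9 to 5.2 bpm.

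SAP 8.4 already shows heart rate and uncorrected QT by arm, so a reader can see a heart-rate difference. This helps, but arm means of QT and HR do not give the mean of a QTc corrected patient by patient. The listings would allow that only by recalculation.

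Fridericia is flat in these figures by construction. If the true QT–rate relation is not the cube root, QTcF will carry its own error, which is a reason to show both.

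A reader might infer three stronger points, which the documents do not support:
- **That the population is tachycardic.** No heart-rate data or heart-rate eligibility criterion is given.
- **That QTc is itself a safety endpoint.** It is one summarised ECG parameter.
- **That the ECGs mostly sample low drug levels.** The Tmax and half-life come from earlier oral-tablet trials. No Tmax is given for dispersed tablets by nasogastric tube in ARDS, and the modelled share below half of peak falls to 28–39% if Tmax is 2 h.

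The documents support only the statement that the ECG schedule does not target peak exposure.

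**Conclusion.** The point holds, and it is modest. Bazett is the sole correction in both documents, and it makes QTcB depend on heart rate by a known factor. Under assumed heart rates of 80 to 120 bpm and a cube-root relation, the within-patient artefact is about 9 to 31 ms. The between-arm artefact is about 4 ms for a 5 bpm difference and zero if mean rates are equal. The direction that matters most is masking, if reparixin lowers heart rate through faster recovery. The primary efficacy analyses are not affected.

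It would be tempting to ask for ECGs timed to the dose as well. That is not pressed here. Last patient last visit was planned for February 2025 (Protocol 3.4) and SAP 2.0 is dated 30 July 2025, so if the timetable held, the ECGs have already been taken.

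**What to change.** **SAP 8.4.** Derive QTcF = QT/(60/HR)^(1/3) for each ECG from the QT and heart rate recorded on it. Summarise QTcF and its change from baseline by arm at each time point as the main QTc result, and include it in the plots and listings. Keep the protocol-named QTcB beside it, so that the two can be compared and the protocol's method is not displaced.

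**SAP 4.11.** Record the addition as a change from the protocol. The documents do not say whether the database has been locked and unblinded. If it has, report QTcF as an added analysis in the CSR, as SAP 4.1 allows.

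**Optional.** Protocol 5.4 has the date and time of each dose entered in the eCRF, and Protocol 6 asks for the actual date and time of all measurements. Where both clock times were captured, list QTcF by time since last dose. This would show how many on-treatment ECGs fell near the expected peak, without assuming a pharmacokinetic model.

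**Cost.** One derived variable with its table rows, plots and listing column; no new data and no burden on sites. The optional listing needs a merge of ECG and dosing times and will have gaps if ECG times are missing.

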8.5 Physical examination

Not applicable

8.6 Other safety evaluations

Not applicable

9. Tables, Figures and Listings

Mock shells for tables, listings and figures are reported in the appendix attached to this document.

9.1 Output conventions

- Each Table, Listing and Figure (TLF) should be numbered, following the ICH E3 Guideline.
- All titles have to be sufficiently explanatory, i.e. the content of the outputs should be clear even when consulted independently from the SAP.

Standard/Forms/Template				
Title		Statistical Analysis Plan Template		
Code		Version	Effective Date	Page
PPD		01	29 Aug 2022	55 of 78

- For numeric variables, units will be presented enclosed in square brackets ([]), when appropriate.
- Each table and each figure should provide reference to the listing where the data on which the table/figure is based are shown.
- Listings should include raw data, i.e. data collected in CRF or other data collection tool, as well as derived data, i.e. data of variables that have been generated for statistical analysis, as applicable.
- Every TLF should report the following information on the upper side of the output:
 - Left aligned:
 - Protocol number
 - Centered aligned:
 - “Confidential”
 - Right aligned:
 - Dompé Farmaceutici SpA
 - Draft/Final Run <date>
- Every TLF should report the following information on the bottom side of the output:
 - Left aligned:
 - the name of the SAS program which will generate the output
 - Centered aligned:
 - Draft/Final Version - Date <date>
 - Right aligned:
 - “Page n of N”, where n is the page number and N is the total number of pages of the document.

9.2 Format requirements

- All TLFs will be produced in landscape format on A4 paper size, unless otherwise specified.
- The titles are centered. The analysis sets are identified on the line following the title.
- it is preferable to use “Courier New” with minimal font size of 8, which is the smallest acceptable point size for the Regulatory Authorities.
- Output files will be delivered in Rich Text Format (RTF) that can be manipulated in Word.

9.3 Table Conventions

- If the categories of a parameter are ordered, then all categories between the maximum and minimum category are presented in the table even in case of frequency equal to 0.
- If the categories are not ordered (e.g., Medical History), then only those categories for which there is at least 1 subject represented in 1 or more groups are included.

Standard/Forms/Template				
Title		Statistical Analysis Plan Template		
Code		Version	Effective Date	Page
PPD		01	29 Aug 2022	56 of 78

- Unless otherwise specified, the estimated mean and median for a set of values are printed out to 1 more significant digit than the original values, and SDs are printed out to 2 more significant digit than the original values.
- Missing descriptive statistics or p-values which cannot be estimated are reported as “-”.

11.1 Derivations and date conventions

11.1.1 Variable derivation

Table 3: Variable derivation rules

Parameter	Calculation
Screened	A patient is considered screened if (s)he has “Date of Written Informed Consent Signature” filled
Screening failure	A patient is considered screening failure if (s)he when “Did the subject complete the study?” is answered “No” on the End of Study Form and Primary reason for study discontinuation = “Screening Failure”
Enrolled	A patient is considered enrolled if (s)he has been screened and (s)he is not a screening failure.
Treatment completed/discontinued	A patient is considered as a treatment completer when : Primary reason for end of treatment is = “Treatment completed” or [Primary reason for end of treatment is = “IMP Discontinuation Criteria” and the criteria specified is = “The patient is discharged home”]. Otherwise, the patient is considered as Treatment discontinued
Change from baseline	Each change from baseline will be defined as difference between the value (minuend) at each post-baseline assessment and the baseline value (subtrahend).
Patient with past disease (medical history)	A patient is considered with past disease if CRF term “Has the patient experienced any past and/or concomitant diseases or past surgeries?” = YES and at least a medical history term has “Ongoing” not flagged. Otherwise the patient is considered as with no past diseases.
Patient with concomitant disease	A patient is considered with concomitant disease if CRF term “Has the patient experienced any past and/or concomitant diseases or past surgeries?” = YES and at least a medical history term has “Ongoing” flagged. Otherwise the patient is considered as with no concomitant disease.
Time from randomization to study discontinuation (days)	End of Study date – Randomization date + 1
Length of study (days)	Last available date – Randomization date + 1

Standard/Forms/Template				
Title		Statistical Analysis Plan Template		
Code		Version	Effective Date	Page
PPD		01	29 Aug 2022	58 of 78

Parameter	Calculation
Last available date	
Most recent visit date/assessment date/procedures date (max: end of study date) defined as follows.
 
last available date = end of study (EOS) date*
 
If reason for discontinuation = “Lost to follow-up”, last available date=most recent visit date§ or assessment date^ or procedures date
 
*For patient who dies: end of study date = date of death
 
§ at Day 60 visits to be considered only if patient Vital Status = “Alive” in the form “Follow-Up”
 
^assessment including information from all summary pages (AEs, CM...)

Last available day	
Last available date – Day 1 date + 1
 
Note: Day 1 date for derivation of the Last available day is based on calendar day (i.e., date of first IMP)

Time from Date of diagnosis of moderate to severe ARDS to randomization	
Randomization date – Date of diagnosis of moderate to severe ARDS + 1.
 
CRF field: “Date of diagnosis of moderate to severe ARDS as defined in inclusion criterion 3” in “ARDS-SPECIFIC INFORMATION” CRF form

Extent of exposure (hours)	
Exposure calculated as total number of hours under treatment: (Date:time of last administration of IMP – Date:time of first administration of IMP)
 
Date/time first and last administration defined in SAP 3.1.1
 
Date/time first administration of IMP missing:
 
If Date first administration of IMP is not missing and time first administration of IMP is missing then:
 
If Date first administration of IMP = “Date of Randomization” and Time randomization is not missing then time first administration of IMP= time of randomization;
 
Otherwise set time first administration IMP = “00:00”
 
Date/time last administration missing:
 
If Time last administration of IMP is missing then set time last administration IMP = “23:59”

Total number of tablets scheduled during the treatment period	
[ROUND(Extent of exposure (hours)/8) + 1]*2
 
The result has to be taken rounded to the closest integer.

Extent of exposure (days)	Date of last administration of IMP – Date of first administration of IMP + 1.

Standard/Forms/Template				
Title		Statistical Analysis Plan Template		
Code		Version	Effective Date	Page
PPD		01	29 Aug 2022	59 of 78

Parameter	Calculation
On treatment period TEAE	
AE start date is on or after treatment start date and on or before end of treatment date.
 
If AE start date is missing and the AE is considered treatment-emergent, it is considered on treatment TEAE.
 
In case of End of treatment date missing or if last IMP intake is after End of Treatment date, the last IMP intake (instead of the End of Treatment) will be considered.

Follow-up period TEAE	
AE start date is after end of treatment date.
 
In case of End of treatment date missing or if last IMP intake is after End of Treatment date, the last IMP intake (instead of the End of Treatment) will be considered.

PaO2/FiO2 ratio	When the PaO2/FiO2 ratio is not reported in the eCRF (i.e. the value is missing) but the two values for PaO2 and FiO2 are available separately, the PaO2/FiO2 ratio will be derived as ratio between the two values.

Standard/Forms/Template				
Title		Statistical Analysis Plan Template		
Code		Version	Effective Date	Page
PPD		01	29 Aug 2022	60 of 78

Primary endpoint "Change in oxygenation index (OI) from baseline to day 7 " [study day based on Date/time]	
OI derivation
 
OI is defined as: % mean airway pressure x FIO2/PaO2, derived as 100 x mean airway pressure x FIO2/PaO2. Following the estimand definition:
 
 - If patient dies before Day 7, or at Day 7 (Day 7 date = Day 1 date + 6, since only date of death -no time- is collected) and OI is missing: OI at day 7 = 90th percentile of the distribution of the primary variable at Day 7. - If patient at Day 7 is extubated* and OI is not evaluable (i.e., if the patient results not intubated* in the time range [First IMP Intake Date/Time +132h, First IMP Intake Date/Time +155h and59 min]): OI at day 7 = 10th percentile of the distribution of the primary variable at Day 7. - Otherwise, OI is set to missing. 
*intubation/extubation status at day 7: check intubations in "Extubation Summary" CRF form. Use the multiple entries of extubation/re-intubation: if the last record of intubations/extubation prior day 7 is an extubation and there are no intubations at day 7, it means the subject was extubated on Day 7. Subjects should reach day 7 to be eligible for this imputation.
 
Collection of data on FiO2/PaO2 and mean airway pressure
 
The implementation of the OI is based on 2 daily forms: "Mechanical Ventilation Parameters" for mean airway pressure, and "Lung Function" for the following parameters: PaO2/FIO2, FIO2, PaO2. FIO2/PaO2, used for the computation of OI, may be derived as 1/(PaO2/FIO2) or by using the individual values of PaO2 and FIO2 (when PaO2/FIO2 is missing) as described in the following section "Missing PaO2/FiO2 or mean airway pressure".
 
Missing PaO2/FiO2 or mean airway pressure
 
In case of missing PaO2/FiO2 for a specific visit, derive it based on the individual values of PaO2 and FiO2, if available. If PaO2 is not available set to missing (PaO2 won't be derived). The same applies for mean airway pressure, if not collected on a specific visit, the OI will be missing for that day.
 
Baseline derivation
 
1 - For each assessment performed on or prior treatment start date/time, derive OI as defined below.
 
1.1 Select the last record of mean airway pressure collected in that day (if on the same date of treatment start date, use only records with time <= time of first exposure to IMP)
 
1.2 - Select the "FiO2/PaO2" which is closest (and non missing) to the selected "mean airway pressure" and occurring on the same timeframe (but assessed on or prior treatment start date/time). Same timeframe here means that it should be considered the date/time of mean airway pressure (detected in step 1.1) +/- 12 hours BUT always considering prior to the first IMP intake. If there is any FiO2/PaO2 available in this timeframe, take that FiO2/PaO2 assessment. If there is no FiO2/PaO2 available in this timeframe, select the FiO2/PaO2 collected in the same exact date of the selected mean airway pressure (selected in step 1.1). If there is no such match, the OI baseline will set as missing.

--	--

Standard/Forms/Template				
Title		Statistical Analysis Plan Template		
Code		Version	Effective Date	Page
PPD		01	29 Aug 2022	61 of 78

Parameter	Calculation
	
2 - Select the OI record closest to the treatment start date.
 
Note: It's expected that the OI will be derived from the assessments performed on the same day of treatment start date (day 1). If OI not available on day 1, then use the OI available from exact previous day (TRTSDT-1). In case neither exists, then the baseline will be missing
 
Note: In case of multiple records, use the value collected under "Randomization/baseline" visit, if available. Otherwise, use the one collected under the latest timepoint prior treatment start date (i.e.: by order: 1 - "Screening", 2 - "Daily assessments through extubation").
 
Post-baseline daily assessments (i.e., assessment after First IMP intake date/time)
 
For each post-baseline assessment, select the value of mean airway pressure based on the study day rules considering date and time. Select the value FiO2/PaO2 based on the study day rules considering date and time. If there is one measurement of mean airway pressure and one measurement of FiO2/PaO2 falling in that specific study day (as defined by the rules considering date/time), select these values to compute the OI at that day. Do the same for each post baseline day. (Example for day 7. Both mean airway pressure and FiO2/PaO2 should be collected in the window [First IMP Intake+132h, First IMP Intake+155h and 59min])
 
For both mean airway pressure and FiO2/PaO2: In case of more assessments at the same day, keep the assessment closer to the midpoint of the time interval. For instance: 2 assessments at day 7 [First IMP Intake Date/Time +132h, First IMP Intake Date/Time +155h and 59 min], the one closer to 144 hours from 1st IMP will be taken.
 
If multiple records exist at the same distance from the midpoint of the time interval, select the first record collected in the eCRF.
 
In case mean airway pressure and/or FiO2/PaO2 is missing at a specific study day, the value of OI for that day is not derived (the 2 records of mean airway pressure and FiO2/PaO2 should be assessed in the same study day, where study day is intended as derived using date/time).

Retrieved drop-out flag for change in OI from baseline to day 7	
For "change in OI from baseline to day 7" the retrieved dropouts are the patients that discontinued the study treatment (treatment completers/discontinuers are defined above in this table under "Treatment completed/discontinued") by day 7 *(day 7 not included) and have the endpoint evaluable by Day 7 (death on the day of the treatment discontinuation not part of the retrieved dropout):
 
Set to 'Y' if Subject discontinued the treatment prematurely by day 7* and patient is alive or have date of death after end of treatment, and the endpoint is not missing for this parameter and timepoint.
 
* date of discontinuation should be prior to the min value for the range of time windows of day 7 (study day using date/time) i.e., discontinuation should happen before First IMP Intake+132h.

Standard/Forms/Template				
Title		Statistical Analysis Plan Template		
Code		Version	Effective Date	Page
PPD		01	29 Aug 2022	62 of 78

Parameter	Calculation
Ventilatory days up to Day 28 [study date based on date/time]	
To derive the number of ventilatory days up to day 28, count the days for which the subject was intubated (from the CRF Form: "Extubation Summary") starting from the date of first IMP intake up to day 28 date, where Day 28 date = Day 1 date/time + 28 days.
 
In case of multiple periods of IMV during the first 28 days, the total duration of ventilation considered all periods of ventilation during the index admission.
 
Between the extubation and the subsequent intubation, there should be $\geq 48h$: if between the extubation and the subsequent intubation there is less than 48h, the extubation (from a clinical point of view) is considered unsuccessful, and it will be considered as a single intubation period (therefore that extubation period should not be considered in the calculation).
 
As all subjects are intubated at the beginning of the study the calculation will be:
 
Time from date/time of first IMP intake to first extubation date/time +
 
Time from second intubation to second extubation (if from first extubation and second intubation there are $\geq 48h$, otherwise Time from first IMP intake to second extubation) +
 
Time from third intubation to third extubation (if from second extubation and third intubation there are $\geq 48h$, otherwise Time from second intubation to third extubation) etc. up to day 28 date/time.
 
Note: the only possible range is the range of real number in the interval $[0, 28]$.

Primary endpoint "Ventilator free days (VFD) at day 28" [study day based on Date/time]	
Number of days from First IMP Intake to Day 28 date when the patient will be alive and free of invasive ventilation[^]. It will be derived as follows:
 
 - Patients who will die before or on day 28: VFD= 0*. - If patient is alive at Day 28 (last available day ≥ 26): VFD = 28 – Ventilatory days up to Day 28 - If subject is alive and followed for < 26 days (last available date < 26) the endpoint is set as missing. 
[^] intubation/extubation status at day 28: check intubations in "Extubation Summary" CRF form.
 
The only possible range of values is between 0 and 28.
 
*In the case subjects are never been extubated: VFD = 0

Retrieved drop-out flag for ventilatory free days at day 28	
For "VFD at Day 28" the retrieved dropouts are the patients that discontinued the study treatment (treatment completers/discontinuers are defined above in this table under "Treatment completed/discontinued") and have the endpoint evaluable by Day 28 (death on the day of the treatment discontinuation not part of the retrieved dropout):
 
Set to 'Y' if Subject discontinued the treatment prematurely and patient is alive or have date of death after end of treatment, and the endpoint is not missing for this parameter and timepoint.

Standard/Forms/Template				
Title		Statistical Analysis Plan Template		
Code		Version	Effective Date	Page
PPD		01	29 Aug 2022	63 of 78

Parameter	Calculation
Change in oxygenation index (OI) from baseline to day 4 [study day based on Date/time]	
The endpoint is derived similarly to change from baseline at day 7.
 
 - If patient dies before Day 4, or at Day 4 (Day 4 date = Day 1 date + 3, since only date of death -no time- is collected) and OI is missing: OI at day 4 = 90th percentile of the distribution of the primary variable at Day 4. - If patient at Day 4 is extubated* and OI is not evaluable (i.e., if the patient results not intubated* in the time range [First IMP Intake Date/Time +60h, First IMP Intake Date/Time +83h and 59 min]), OI at day 4 = 10th percentile of the distribution of the primary variable at Day 4. - Otherwise, OI is set to missing. 
*intubation/extubation status at day 4: check intubations in "Extubation Summary" CRF form. Use the multiple entries of extubation/re-intubation: if the last record of intubations/extubations prior day 4 is an extubation, and there are no intubations at day 4, it means the subject was extubated on Day 4.

ICU stay up to Day 28 and up to hospital discharge (days)	The information on ICU length of stay is collected under "Other Clinical Event Form" at Day 28 Visit and at Hospital Discharge Visit

Standard/Forms/Template				
Title		Statistical Analysis Plan Template		
Code		Version	Effective Date	Page
PPD		01	29 Aug 2022	64 of 78

Parameter	Calculation
ICU-free days at Day 28 and at hospital discharge (days) [study day based on Date]	
ICU-free days at Day 28
 
If patient is alive at Day 28 (last available day \geq 26) and ICU-free days is not missing at Day 28: ICU-free days = 28 – ICU stay up to Day 28.[^]
 
Else, If patient is discharged before Day 28 (date of discharge is not missing and date of discharge $<$ Day 28) and the patient died after hospital discharge and before day 28 (hospital discharge $<$ date of death $<$ Day 28) then ICU-free days at day 28= ICU-free days at discharge
 
If patient dies within Day 28 : ICU-free days = 0
 
If subject is alive and followed for $<$ 26 days (last available date $<$ 26) the endpoint is set as missing.
 
Otherwise, the endpoint will be set as missing.
 
[^]in case of negative values, it is assumed that ICU-free days = 0.
 
Day 28= Day 1 date + 27
 
ICU-free days at Hospital Discharge
 
If patient is alive at hospital discharge date* (last available date $>$ hospital discharge date*): ICU-free days = [hospital discharge date* – First IMP Intake date + 1] – ICU stay up to hospital discharge date*. [^]
 
If patient is never discharged (date of discharge is missing) and the patient died after day 28 (date of death $>$ Day 28), then ICU-free days at discharge=ICU-free days at day 28
 
Else (If patient dies within hospital discharge date*) or (if date of death is not missing and it is prior to Day 28 (date of death $<$ Day 28) and discharge date is missing (i.e., subjects died during hospitalization)): ICU-free days = 0
 
Otherwise, the endpoint is set as missing.
 
[^]in case of negative values, it is assumed that ICU-free days = 0.
 
*date of discharge is collected in End of Study form; in the case it is missing it is taken from Visit date in "Hospital Discharge".

Standard/Forms/Template				
Title		Statistical Analysis Plan Template		
Code		Version	Effective Date	Page
PPD		01	29 Aug 2022	65 of 78

Parameter	Calculation
Hospital stay up to Day 28 (days) [study day based on Date]	
Hospital stay up to Day 28 :
 
Date of discharge* – First IMP Intake date + 1.
 
If Date of discharge* is after Day 28 date, then Day 28 date will be used instead.
 
If Date of discharge* is missing and date of death\geq Day 28 date then date of Discharge = Day 28 date.
 
If Date of discharge* is missing and last available day \geq 26 then date of Discharge = Day 28 date.
 
Otherwise the endpoint is set as missing.
 
Day 28 date: Day 1 date + 27
 
*date of discharge is collected in End of Study form; in the case it is missing it is taken from Visit date in "Hospital Discharge".

Hospital-free days by Day 28 [study day based on Date]	
Hospital-free days by Day 28
 
If patient is alive at Day 28 (last available day \geq 26): Hospital-free days = 28 – Hospital stay up to Day 28
 
If patient dies within Day 28: Hospital-free days = 0
 
Otherwise, If subject is alive and followed for $<$ 26 days (last available day $<$ 26) the endpoint is set as missing.
 
Day 28= Day 1 date + 27

Standard/Forms/Template				
Title		Statistical Analysis Plan Template		
Code		Version	Effective Date	Page
PPD		01	29 Aug 2022	66 of 78

Parameter	Calculation
Patients discharged (alive) by Day 28 [study day based on Date]	
A patient is considered discharged alive by Day 28:
 
 - if patient is discharged* before Day 28 (included) (regardless the vital status after discharge). 
Otherwise, a patient is considered not alive and discharged by Day 28:
 
 - if patient dies and date of discharge* is missing, OR - if patient is not discharged* before Day 28 (included) (day of discharge >28) OR - if date of discharge is missing, but subject is in study long enough (last available day ≥ 26) OR - Discharge date=Death date (assumptions: patient died in the hospital) 
Otherwise, if the date of discharge is missing and subject is alive and followed for <26 days (last available date<26) the endpoint is set as missing.
 
Day 28: Day 1 + 27
 
*date of discharge is collected in EOS; in the case it is missing it is taken from Visit date in "Hospital Discharge".

